## Study protocol

This dissertation was a non-experimental correlational quantitative analysis of multi-clinic site locations of consecutive patients referred to or coming via direct access for physical therapy care related to chronic low back pain. It was a collection of trust surveys, TA questionnaires, and patient reported outcomes related to their low back pain and function completed by the patient participant through an interrupted time-series of prior to initial evaluation, post-initial evaluation, and at discontinuation of the current episode of care. The physical therapist participants completed a patient connection and engagement questionnaire after the second visit and at discharge along with outcomes measurement data collect at the completion of the current episode of care. Data collection was at multiple outpatient physical therapy sites with multiple physical therapists and wide patient demographics to improve generalizability of the study findings.

The research project was conducted according to the Declaration of Helsinki. All the participants were fully informed of the study content before their participation in this study and completed informed consent. Institutional Review Board (IRB) at the University of South Dakota served as the IRB of record with joint approval from Nova Southeastern University IRB.

### **3.3 Procedures**

#### **3.3.1 Participant recruitment**

Various clinic sites (AZ, CA, RI, VA, WA, and WI) were approached through email, phone, and direct contact and were provided general study protocol to investigate their interest in serving as a data collection site. Clinic sites interested in participating completed an IRB Location Site Application along with a clinic site consent agreement (Appendix A). Each clinic site had a point of contact person appointed, and that contact person ensured that all informed

consent forms were signed for those physical therapists willing to consent to participate in the study protocol. Once each clinic site and participating physical therapists at those sites were set up, new patients potentially meeting inclusion criteria of chronic low back pain (pain greater than 3 months) coming to the clinic were identified by front office staff scheduling the appointment. Upon arrival at the clinic, potential patient participants were handed regular clinic site new patient paperwork, but they were also given a participant recruitment flier. If the patient verbally expressed interest in participation, they were provided with an introductory letter with a PsychData link. This link had the informed consent and the participant was given a Health Insurance Portability Accountability Act (HIPAA) form as part of the IRB process. This method of recruitment was utilized to minimize any potential coercion.

Once patient participants completed the informed consent process they were directed to a second PsychData link in order from them to complete a participant demographics form (Appendix B) that further verified their eligibility into the study. Inclusion criteria consisted of greater than 18 years of age, able to read, speak, and write in English, and presence of low back pain for at least 3 months. Exclusion criteria were current pregnancy or active cancer diagnosis. Patient participants were also excluded from the study if at any point during the episode of care they required different medical attention beyond physical therapy and needed to be referred out for medical reasons and had to discontinue their physical therapy prior to achieving goals. Any patient participant that did not receive at least 80% of the treatments from the initial physical therapist participant were excluded from primary data collection. Physical therapist participant inclusion criteria were having a physical therapy license to treat patients and employed at a clinic site approved for the study.

The initial *a priori* was set for a total of 64 patient participants with the primary complaint of chronic low back pain that had lasted a minimum of 3 months prior to initiating the current physical therapy episode of care. The patient were consecutively enrolled in the study at the various clinic sites. An *a priori* achieves 79% power to detect a Pearson correlation of 0.400 using a two-sided hypothesis test with a significance level of 0.05 with an included 20% dropout rate. These results are based on 1000 samples from the bivariate normal distribution under the alternative hypothesis. The number of physical therapist participants was determined by the clinic site enrollment and treating at least one patient participant during the course of the study.

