informed consent, they progressed to additional PsychData questionnaires to be filled out by the patient participant prior to their initial evaluation with their physical therapist. Information collected consisted of: baseline demographic information sheet, General Trust in Physician Scale, Trust in Physician Scale, PCAS, Wake Forest Scale, ODI, and NPRS. The online participant data collection allowed for blinding of the physical therapist throughout the study to the trust measurement scores. Patient participants received normal physical therapy evaluation and treatment as directed by the physical therapist. Upon completion of the initial visit, the patient participant completed the WAI-SR, Trust in Physician Scale, PCAS, and Wake Forest Scale through a second PyschData link. After completion of the second physical therapy visit, the participating physical therapist completed the PT Survey of Patient Connection and Engagement. Patient participants were blinded to the physical therapist's responses on this instrument. Patient participants continued to receive normal physical therapy as directed by the physical therapist working toward discontinuation of the current episode of care. The majority of the physical therapy encounters (80%) needed to have the initial physical therapist directly involved with the care of the patient participant to be eligible for data collection. If less than 80% of the visits have the direct care delivered by someone other than the initial physical therapist, that data was excluded from primary analysis. Upon discontinuation of the current episode of care or the end of 6 months of care, the patient participant completed the Trust in Physician Scale, PCAS, Wake Forrest Scale, WAI-SR, ODI, NPRS, and GROC. The participating physical therapist completed a second PT Survey of Patient Connection and Engagement at the conclusion of care. (Figure 1) Patient participants that complete all three series of forms (pre-initial visit, post-initial visit, and discontinuation episode) were eligible for a total of \$25 in Walmart gift cards to be mailed to an address of their choice.

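### The 80% same-therapist rule excludes patients after trust has been measured, and the SAP has no analysis that shows whether the trust–outcome correlation depends on it

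*Combined protocol and SAP*

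**What the plan says.** The rule is stated three times, in three ways.

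- Section 3.3.1: "Any patient participant that did not receive at least 80% of the treatments from the initial physical therapist participant were excluded from primary data collection". The base is treatments, and the patient leaves data collection.
- Section 3.3.5, first statement: 80% of encounters "needed to have the initial physical therapist directly involved with the care of the patient participant to be eligible for data collection". The base is encounters, and again eligibility for data collection is at stake.
- Section 3.3.5, next sentence: "If less than 80% of the visits have the direct care delivered by someone other than the initial physical therapist", then "that data was excluded from primary analysis". The base is visits, and the consequence is now exclusion from the primary analysis only. Read literally, this sentence removes patients who mostly stayed with their first therapist, the reverse of the other two statements.

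Section 3.3.5 also fixes the timing. Trust is measured before the first visit, after the first visit and at the end of care (or at 6 months). Pain and function (NPRS, ODI) are measured before the first visit and at the end; the global change rating is taken at the end only.

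The SAP makes Spearman's rho between trust and outcome the primary statistic. It does not mention the 80% rule and defines no analysis set. It plans no comparison of kept and excluded patients and no analysis that includes the excluded ones.

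**The concern.** Whether a patient meets the rule is settled during the episode, after two of the three trust measurements. A patient who distrusts the first therapist, or who is not improving, may change therapist and so leave the primary set. Staying may therefore be partly a consequence of the predictor, and perhaps of the course of the outcome, in a study that asks how the two are related. Selection of this kind can change a correlation even when every retained score is accurate.

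A percentage rule also acts differently on episodes of different length, because visits come in whole numbers.

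Three things are at stake: the size of the primary correlation, how far it applies beyond patients treated mainly by one therapist (the study protocol cites generalizability as a reason for using many sites), and whether a reader can judge either. If the excluded patients' discharge forms were never collected, the question cannot be answered afterwards.

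**Working it through.** **Inputs from the documents (section 3.3.1).** The sample size "was set for a total of 64 patient participants", with "79% power to detect a Pearson correlation of 0.400 using a two-sided hypothesis test with a significance level of 0.05" and a 20% dropout allowance. The documents give no exclusion rate, no visit counts and no reasons for changing therapist. All such values below are assumptions.

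**1. The plan's own figure.** Evaluable patients: 64 × 0.80 = 51.2, so 51. Simulating the Spearman test on bivariate normal data with r = 0.40, n = 51 and two-sided 0.05 gives about 79–80% power. This reproduces the stated 79%. (A Pearson test by Fisher's z at n = 51 gives 83.5%.)

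**2. Effect of selection on rho.** The true Spearman rho is (6/π) × arcsin(0.40/2) = 0.38. I simulated large bivariate normal samples, with outcome scored so that higher is better. Patients were excluded either by a logistic model (odds ratios per SD) or by a hard cut, and rho was computed in those kept.

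| What drives exclusion | 10% excluded | 20% excluded |
|---|---|---|
| Unrelated to trust or outcome (e.g. scheduling) | 0.38 | 0.38 |
| Low trust only, odds ratio 4 | 0.37 | 0.36 |
| Exactly the lowest-trust patients | 0.33 | 0.30 |
| Low trust and poor outcome, odds ratio 2 each | 0.35 | 0.32 |
| Low trust and poor outcome, odds ratio 3 each | 0.32 | 0.28 |
| Low trust and good outcome, odds ratio 2 each | 0.40 | 0.42 |
| Low trust and good outcome, odds ratio 3 each | 0.42 | 0.45 |

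The last two rows would arise if, for example, patients who were doing well were handed to another clinician. Across all rows the range is 0.28 to 0.45.

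**3. Effect on power, holding n at 51.** With log-odds of 1 per SD on both variables (odds ratio about 2.7 each), power at 10% and 20% exclusion is 64% and 52% when low trust and poor outcome drive exclusion. It is 86% and 90% when low trust and good outcome do. The plan does not say whether its 20% allowance covers these exclusions. If they come on top of it and are unrelated to trust, n falls to 45 (51 × 0.9 = 45.9) or 40 (51 × 0.8 = 40.8), and power to 74% or 68%.

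**4. Episode length.** An episode of v visits may include at most floor(0.2 × v) visits with another therapist: 0 for 1–4 visits, 1 for 5–9, 2 for 10–14. Assume that the first visit is with the initial therapist and each later one is covered by someone else with probability p. Then P(excluded) = P(Bin(v − 1, p) > floor(0.2 × v)).

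| Visits | 1 | 2 | 3 | 4 | 5 | 9 | 10 | 14 | 20 |
|---|---|---|---|---|---|---|---|---|---|
| p = 0.10 | 0% | 10% | 19% | 27% | 5% | 19% | 5% | 13% | 3.5% |

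At 4 visits this is 1 − 0.9³ = 27.1%. With p = 0.20 the figures are 49% at 4 visits, 18% at 5, 50% at 9, 26% at 10 and 50% at 14. The pattern is a saw-tooth. Episodes of 2–4 visits have no tolerance at all, and a one-visit episode can never fail.

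**The case against.** The rule has a sound rationale. According to section 3.3.2, the provider-specific scales were reworded to refer to the patient's physical therapist. If several therapists deliver the care, it becomes unclear whom the discharge scores describe and whose care produced the outcome. The association among patients treated mainly by one therapist is a defensible target.

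Making all enrolled patients the primary set could also do harm. Assume trust-only exclusion (odds ratio 4 per SD, 10–20% excluded) and a trust–outcome correlation of 0 to 0.2 in those who changed therapist. Rho in all patients is then about 0.28–0.35, against 0.36–0.37 in the kept set, so the kept set lies closer to 0.38. This argument stands, and it is why the 80% set should remain primary.

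A reader might infer that the rule necessarily under-represents low-trust patients and biases the correlation toward zero. The documents do not support that: they give no reason for any therapist change, scheduling alone produces no bias, and some selection patterns raise rho. A reader might also infer that short episodes are penalized across the board. The saw-tooth contradicts this, and the documents give no visit counts.

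Finally, the last statement of the rule in 3.3.5 implies that the excluded patients' data exist. That is a fair reading, but section 3.3.1 and the preceding sentence of 3.3.5 say otherwise, so the matter is open.

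None of this answers the remaining gap: the plan has no way to show whether the selection mattered.

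**Conclusion.** The concern holds as a point about an unexamined post-baseline exclusion, not as proof of bias in a known direction. Under assumed exclusion of 10–20%, a true Spearman rho of 0.38 could appear as anything from about 0.28 to 0.45. Selection on trust alone has a modest effect (0.36–0.37) unless it is close to a hard cut (0.30–0.33). The larger shifts in either direction require exclusion to depend on outcome as well. These ranges rest on bivariate normality and on assumed exclusion rates and strengths, none of which the documents give.

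Two parts need no assumption. The SAP contains no analysis of the excluded patients. The statements of the rule conflict on its base, its consequence and, in one sentence, its direction, so as written the primary set is not uniquely defined.

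**What to change.** First reconcile sections 3.3.1 and 3.3.5 into one statement of the rule: one base (treatments, encounters or visits), one direction and one consequence. Then:

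1. State that all three series of forms are collected from every enrolled patient, whoever delivers the later visits, so that the rule affects only the analysis set. If collection has already closed, state whether these forms exist.
2. Keep the 80%-continuity set as primary and name it in the SAP. Add a prespecified sensitivity analysis that repeats the trust–outcome Spearman correlations in all enrolled patients with discharge outcomes. Use post-initial-visit trust as the predictor, since it refers to the initial therapist even for a patient who later changes.
3. Report how many patients the rule excludes, with reasons, and compare pre-visit and post-initial-visit trust between kept and excluded patients.

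The cost is a small amount of extra form collection, one further run of the same correlations and one descriptive table. The all-patients result will include mixed-therapist care, which may dilute the association, so it should be read beside the primary result and not in place of it.

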### **3.3.2 Instruments – Predictor variables**

Various instruments were used to measure trust during the encounter. For the purpose of this study, three of the most well studied provider-specific trust measurement scales (Trust in Physician Scale, Primary Care Assessment Survey (PCAS), and Wake Forest Scale) used in the physician and psychology literature were chosen that have items written that could easily translate to physical therapy practice and patient care. To date, none of these provider-specific trust measurement scales had been studied for use in physical therapy practice. General trust in the medical profession and physical therapy was assessed by the General Trust in Physician Scale. A TA measurement scale (Working Alliance Inventory – Short Revised) was used and was the only predictor instrument previously used in the physical therapy literature. The final instrument was developed as part of the dissertation process to assess the physical therapist's perception of their patient's connection and engagement (PT Survey of Patient Connection and Engagement) within the therapeutic process during the physical therapy encounter.

Trust in Physician Scale: The Trust in Physician Scale is one of the first instruments developed to assess a patient's interpersonal trust in their physician. The original published work

of Anderson and Dedrick in 1990, detailed the development and validation of the Trust in Physician Scale. Three different dimensions of trust were assessed: dependability of the physician, confidence in the physician's knowledge and skills, and confidentiality and reliability of information between the physician and patient. The Trust in Physician Scale is a patient self-report tool with 11-items scored on a 5-point Likert scale. The labels for the Likert scale followed the later modified version by Thom, et al. (1 = totally disagree, 2 = disagree, 3 = neutral, 4 = agree, 5 = totally agree). Raw scores can range from 11 to 55 with higher scores demonstrating higher trust. The scale was modified for the purposes of this study with the words "physical therapist" inserted any place the original version had the word "doctor". It has a combination of positively (questions #2, 3, 4, 6, 8, 9, and 10) and negatively (questions #1, 5, 7, and 11) worded questions. The Flesch reading ease score equates to 52.3 to provide a Flesch-Kincaid grade level at 9.6 according to Microsoft® Word 365 for Office (Redmond, WA). This scale has been used in research in primary care physicians and specialty medical practice with a variety of patient populations. (Appendix C)

Primary Care Assessment Survey: The PCAS was developed to measure seven different domains of care through 11 different summary scales. The trust summary scale assesses the physician's integrity, competence, and role as the patient's agent. The trust summary scale is measured with eight different item questions with a lowest score of 8 and maximal score of 40, with the higher score demonstrating more trust. Seven of the item questions (questions #1-7) are measured by a five-point Likert scale (1 = strongly agree, 2 = agree, 3 = not sure, 4 = disagree, 5 = strongly disagree). Question #8 is scored on a 11-point scale with anchors (0 = not at all, 10 = completely) it requires recalibration to align with questions #1-7 (1 = 0-2 precoded item value, 2 = 3-4 precoded item value, 3 = 5-6 precoded item value, 4 = 7-8 precoded item value, 5 = 9-10

precoded item value). Four of the seven Likert scale items (questions #1, #3, #5, #8) are reverse score items and must be recoded for final scoring (5 = precoded item value 1, 4 = precoded item value 2, 3 = precoded item value 3, 2 = precoded item value 4, 1 = precoded item value 5). For purposes of this study, the word “doctor” was replaced with “physical therapist” from the original scale. The PCAS scoring algorithms calculate a score if a respondent answers at least 50% of the items on the scale (4 items on the trust scale), the missing whole values are inputted as the respondent’s average score across all completed items for the scale. A transformed scale score can be computed as the product of the actual raw scale score minus the lowest possible raw scale score (8 on the trust scale) that is divided by the possible raw scale score range (32 on the trust scale) multiplied by 100. The Flesch reading ease score is 62.6, which equates to an 8.4 Flesch-Kincaid grade level according to Microsoft® Word 365 for Office (Redmond, WA). The scale was originally developed and tested on Massachusetts state employees on their level of trust with their primary care physician. (Appendix D)

Wake Forest Scale: The third provider specific trust measurement scale used was the Wake Forest Scale developed by Hall, et al. The Wake Forest Scale was developed to improve on the various trust measurement scales that currently had been published at that time (Anderson/Dedrick with the Thom modification, Safran, and Kao) and to be more generalized to other care providers, not just physicians. The Wake Forest Scale development was done by retaining or modifying questions from the existing scales that fit their conceptual model of trust measurement. To address areas of the trust domain that the study team did not think were fully covered, they, along with a group of experts developed additional items. After initial testing and screening of questions, it produced 26 candidate items for further testing, which ultimately produced the final 10-items that were accepted for the scale. The 10 items reflect

dimensions of trust (fidelity = #1-2, competence = #3-4 and #8, honesty = #6, global = #5, #7, and #9-10). The items cover question format consisting of a mixture of positive (#1, #4-7, and #9-10) and negative (#2, #3, and #8) statements in Likert categories (1 = strongly disagree, 2 = disagree, 3 = neutral, 4 = agree, 5 = strongly agree). Trust is measured with a sum of the 10 item scores, with reverse scoring for negative items, to produce a range of scores from 10 to 50, with higher scores demonstrating higher levels of trust. For purposes of this study the questions with the words “your doctor” were replaced with “your physical therapist”. The final Flesch reading ease is 54.0, demonstrating a Flesch-Kincaid grade level of 9.6 according to Microsoft® Word 365 for Office (Redman, WA). (Appendix E)

General Trust in Physician Scale: Patient general trust in healthcare providers has been shown to be different than interpersonal healthcare provider trust. Thus general trust potentially has a strong influence on the formation of interpersonal trust and was measured prior to the initial visit for the purpose of this study with the General Trust in Physician Scale. This scale was developed to test general trust in physicians in contrast to other scales that assess individual physician trust. An 11-item scale was formulated from the initial 25 candidate items that were based on five domains (fidelity, competence, honesty, confidentiality, and global trust). Five-point Likert scale categories were utilized for each question (1 = strongly disagree, 2 = disagree, 3 = neutral, 4 = agree, 5 = strongly agree). The final 11-items have both positive (#1, #3-6, and #8-10) and negative (#2 and #7) worded questions, with reverse scoring for negative items. Scores can range from 11 to 55, with higher scores demonstrating higher trust. If one or two scores were left out, the missing values were imputed with the average score, if three or more scores were missing the total score was not be calculated and left out. The words “physical therapists” were inserted for the word “physician” for use with this study. The General Trust in

Physician Scale according to Microsoft® Word 365 for Office (Redman, WA) has a Flesch reading ease of 42.4 providing a Flesch-Kincaid grade level of 10.8. (Appendix F)

Working Alliance Inventory-Short Revised: The Working Alliance Inventory-Short Revised (WAI-SR) is one of the most commonly used instruments to measure the alliance between patients and therapists in physical rehabilitation. A 12-item short form was originally developed in 1989 from the original 1986 36-item Working Alliance Inventory and revised in 2006 into the current WAI-SR. The WAI-SR has been developed to assess Bordin's Task, Goal, and Bonds dimensions. The scale is measured on a 5-point Likert scale (1 = never, 2 = rarely, 3 = sometimes, 4 = often, 5 = always). All items are positively worded and higher scores reflect higher levels of therapeutic alliance. Flesch reading ease score is at 63.0, producing a Flesch-Kincaid grade level of 8.0 according to Microsoft® Word 365 for Office (Redman, WA). (Appendix G)

PT Survey of Patient Connection and Engagement: This survey questionnaire was developed for use during this dissertation study. An original 10-question survey was developed and created based on current literature in the area of TA along with personal conversation with experts in the field of physical therapy and patient care management. After original survey item creation was completed, it was sent to a panel of five clinicians throughout the US that have experience in research and the study of patient involvement and psychosocial aspects of clinical care from both practice and academic settings. After review of the questionnaire and the comments made by the panel, it was revised into its current consensus form. This questionnaire is aimed to evaluate the physical therapist's perceptions of the patient's engagement and connection with their physical therapist during the therapeutic encounter. No measurement tool such as this exists based on the review of the current literature. The scale

contains 10 positively worded items scored on a 5-point Likert scale (1 = very poor, 2 = below average, 3 = average, 4 = above average, 5 = excellent). The score contains two sub-scores connection (questions 1, 3, and 7) and engagement (questions 2, 4-6, and 8-10). The questionnaire scores a 62.0 on the Flesch reading ease scale, making it at an 8.5 Flesch-Kincaid grade level according to Microsoft® Word 365 for Office (Redman, WA). (Appendix H)

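### The PCAS trust-scale scoring key contradicts itself: it counts four reversed Likert items but lists three, plus the 0–10 item #8

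*Combined protocol and SAP*

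**What the plan says.** The scoring of the PCAS trust scale is described in section 3.3.2, in the Primary Care Assessment Survey paragraphs.

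- **Total.** Eight items are summed, "with a lowest score of 8 and maximal score of 40, with the higher score demonstrating more trust".
- **Likert items.** "Seven of the item questions (questions #1-7) are measured by a five-point Likert scale", coded "1 = strongly agree, 2 = agree, 3 = not sure, 4 = disagree, 5 = strongly disagree". Agreement is therefore the low code.
- **Item #8.** "Question #8 is scored on a 11-point scale with anchors (0 = not at all, 10 = completely". Its answers are then regrouped in ascending order to match the other seven items, from 0–2 becoming 1 up to 9–10 becoming 5.
- **Reversal.** "Four of the seven Likert scale items (questions #1, #3, #5, #8) are reverse score items and must be recoded for final scoring", using the map that begins "5 = precoded item value 1, 4 = precoded item value 2, 3 = precoded item value 3".
- **Missing items.** The algorithm will "calculate a score if a respondent answers at least 50% of the items on the scale", with gaps filled by the respondent's own mean.
- **Transformation.** Raw score minus 8, divided by 32, times 100.

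The section refers to Appendix D for the instrument. The wording of the items is not in the text available for this review.

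**The concern.** The reversal sentence cannot be squared with the item description before it. If the Likert items are #1 to #7, then #8 is not one of them, and the sentence names three Likert items while claiming four. The two obvious repairs are not equivalent. If #8 is a misprint, some other Likert item is reversed and #8 is left alone. If the count or label is loose, #8 may be reversed as listed, or the true number may be three.

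The direction of #8 is what makes this more than a slip of wording. A Likert item on which agreeing shows trust starts out coded low and needs reversing. Item #8 is recalibrated the other way, with *completely* at the top. Whether a further reversal puts it in line with the scale or against it depends on what the item asks.

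PCAS is one of three provider-specific trust scales and is collected before the initial visit, after it, and at the end of care (section 3.3.5). Under the SAP the individual trust scores enter the Spearman correlations with outcomes, with the alliance inventory and with the therapist survey, the Friedman test over time, and the linear regressions. A wrongly keyed item would work against the rest of the scale in all of these. None of the trust scales had been studied in physical therapy before, so a weaker PCAS result could be mistaken for a property of the instrument.

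**Working it through.** **Inputs**, all from section 3.3.2: eight items, each ending on 1–5; Likert set #1 to #7; reversal list #1, #3, #5, #8; #8 recalibrated as 0–2 → 1, 3–4 → 2, 5–6 → 3, 7–8 → 4, 9–10 → 5; reversal of a value v is 6 − v; transformed score = (raw − 8)/32 × 100.

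**1. The plan's own range.** 8 × 1 = 8, 8 × 5 = 40, and 40 − 8 = 32. The stated range and width reproduce.

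**2. Count against list.** Of #1, #3, #5 and #8, those within #1 to #7 are #1, #3 and #5. That is three, not four.

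**3. Item #8 under the printed steps.** The reversal map covers 1–5 only, so for #8 it can apply only after recalibration:

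| Answer | Recalibrated | Then reversed |
|---|---|---|
| 0–2 | 1 | 5 |
| 3–4 | 2 | 4 |
| 5–6 | 3 | 3 |
| 7–8 | 4 | 2 |
| 9–10 | 5 | 1 |

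The steps can be carried out in sequence, but *completely* ends at 1.

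**4. Can the range identify the key?** No. Every item spans 1–5 whether or not it is reversed, so the attainable total is 8–40 under any key.

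**5. Totals under the candidate keys.** Take a respondent who gives the most trusting, or the least trusting, answer to every item. Assume that agreeing with #1, #3 and #5 shows trust, and let k be a possible fourth such Likert item. Cells show raw totals for most / least trust.

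| True item directions | Key 1, 3, 5, 8 (as listed) | Key 1, 3, 5 | Key 1, 3, 5, k |
|---|---|---|---|
| No k; 10 on #8 = high trust | 36 / 12 | 40 / 8 | 36 / 12 |
| No k; 10 on #8 = low trust | 40 / 8 | 36 / 12 | 32 / 16 |
| k exists; 10 on #8 = high trust | 32 / 16 | 36 / 12 | 40 / 8 |
| k exists; 10 on #8 = low trust | 36 / 12 | 32 / 16 | 36 / 12 |

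Each of the three keys is right in one row and wrong in the other three. In the last row none is right.

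**6. Size per wrongly keyed item, all items answered.** At either extreme, 5 − 1 = 4 raw points, and 4/32 × 100 = 12.5 transformed points.

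- One item: 7 × 5 + 1 = 36, transformed 28/32 × 100 = 87.5, instead of 40 (100). At the low end, 7 × 1 + 5 = 12 (12.5) instead of 8 (0).
- Two items: 6 × 5 + 2 × 1 = 32 (75) and 6 × 1 + 2 × 5 = 16 (25).

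**7. Missing-item rule.** Filling gaps with the respondent's mean spreads a keying error. A fully trusting respondent with four answers, one of them wrongly keyed, has mean (5 + 5 + 5 + 1)/4 = 4 and total 8 × 4 = 32 (75), instead of 40 (100).

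**8. Effect on correlations and change over time.** An item scored against the others weakens the total as a measure of trust. By how much depends on the inter-item correlations and the spread of answers. The documents give neither, so no figure is put on it.

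**The case against.** The strongest reply is that the reversal list appears only once and names #8 explicitly. The earlier description of the items says nothing about which are reversed. Read the phrase as four of the eight items, and the key runs from start to finish and gives the stated range. On that reading the only fault is a loose label. The anchors of #8 would suit a positive or a negative stem, and aligning it with the other items may mean no more than reducing eleven categories to five. Appendix D may make the direction of every item plain, and its absence here is not a gap in the plan. The other two provider-specific scales have their own item directions in the text and do not depend on this key.

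Most of this stands. It rules out three inferences that a reader might draw:

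- **That #8 should not be reversed.** The anchors and the upward recalibration hint at it, but the only explicit statement says the opposite, and the item wording is not shown.
- **That a fourth Likert item was left unreversed.** This is one possible reading of the count, not something the text establishes.
- **That the PCAS results are attenuated by some stated percentage.** Any such figure needs assumed loadings and response distributions, as well as a scoring error that nobody has shown.

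The contradiction itself survives. The sentence calls #8 a Likert item, which the item description excludes, so its listing of #8 cannot be taken as settled. No other text available corrects it.

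**Conclusion.** The point holds as an inconsistency in the written scoring key that should be fixed. That the count and the list disagree is certain from the text alone. Which of them is wrong cannot be decided from the text, and the stated range does not help.

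The consequence is conditional. If the key applied was wrong, each wrongly keyed item costs a respondent at either extreme 4 raw or 12.5 transformed points, and more where missing items are filled in. PCAS correlations and changes over time would then be weakened by an amount the documents do not fix. Nothing is mis-scored if #8 is a misprint and the intended Likert item was reversed, if the count should be three and #8 was left alone, or if #8 is negatively worded and no further Likert item needed reversing.

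A reader might infer that the trial's PCAS data were scored wrongly. The documents do not support that, because they do not show which key was run in SPSS. The table of totals assumes that #1, #3 and #5 are correctly listed as reversed.

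**What to change.** 1. Check the item wording in the instrument as administered (Appendix D).
2. Rewrite the reversal sentence in section 3.3.2 to give the direction of each of the eight items, say whether #8 is reversed after recalibration, and make the count and list agree.
3. Confirm which key was used in SPSS, and check that each recoded item correlates positively with the sum of the other seven. A negative correlation would point to a wrongly keyed item.
4. Only if that key was wrong, rescore PCAS at all three time points, including imputed items, and rerun the PCAS Spearman, Friedman and regression analyses. If it was right, only the text changes.

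The certain cost is one sentence and one check of the scoring key. Rescoring needs item-level answers. The missing-item rule needs them too, but the documents do not say whether they were kept.
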